5.4.11.3 Physical Examination

Comprehensive physical examination will be performed at Screening and Study Exit Visits.

The physical examination will include assessment of the following systems: General Appearance, Skin, Head and Neck, Mouth, Lymph nodes, Thyroid, Abdomen, Musculoskeletal, Cardiovascular, Respiratory and Neurological. Each body system examined will be characterized as Normal or Abnormal.

Physical examination findings will be summarized by visit. The number and percentage of subjects with normal and abnormal findings will be presented for each body system. Additionally, a shift table comparing the Screening and Study Exit evaluations will be created.

All physical examination data will be provided in a listing.

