#### 5.3.2. Subjects who prematurely discontinued the study

##### *5.3.2.1. Early discontinuation due to consent withdrawal*

In case of withdrawal of consent, the date of withdrawing consent will be collected. If possible, the reason for withdrawing consent will be collected to exclude safety reason. No additional data will be collected from the time of consent withdrawal.

*5.3.2.2. Early discontinuation for reason other than withdrawing consent*

The investigator will make every effort to complete the following at the time of study discontinuation.

1. Reason for early discontinuation.
2. Comprehensive Physical Examination.
3. Vital signs (pulse, blood pressure, temperature, and respiration rate).
4. ECOG Performance Status.
5. Clinical labs (Appendix 13-4).
6. Serum  $\beta$ -HCG (only for female subjects of childbearing potential).
7. Concomitant medications and adverse events.

---

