##### 10.5.3. Safety Analysis

Safety analysis will be performed on the Safety Population.

The number and percentage of subjects with normal and abnormal findings will be provided for each physical examination in a shift table comparing screening and the end of study evaluation.

Vital signs will be summarized descriptively (mean, standard deviation, median, minimum and maximum). Change from baseline will also be summarized.

Skin photosensitivity is an adverse event of special interest and will be summarized separately from other adverse events at each safety assessment. Changes in skin will be assessed by grade of erythema, edema and blistering. The data will be tabulated by CTCAE grade in the Dermatology/Skin category.

Descriptive statistics for each clinical laboratory test will be presented for the baseline and the end of study assessment. Change from baseline will also be summarized. According to the laboratory normal ranges, laboratory test results will be categorized as low (< lower limit of normal, LLN), normal (within normal range), and high (> ULN). Shift tables, comparing the distributions of these three categories at baseline versus the end of study assessment, will be presented.

---

Concomitant medications will be coded using the WHO Drug dictionary. Medications initiated prior to start of treatment and maintained during the study, or taken during the course of the study will be considered as concomitant medications. Concomitant medications will be summarized according to the preferred terms only.

Adverse events will be coded using the Medical Dictionary for Regulatory Activities (MedDRA). The number and percentage of subjects who experienced any AEs as well as serious AEs will be presented by system organ class (SOC) and by preferred term (PT) within SOC. All AEs will be similarly presented by intensity (mild, moderate, severe or using the CTCAE grading system) and by relationship to treatment (reasonable possibility/no reasonable possibility). One-sided 95% confidence limit will be computed for each AE percentage via exact binomial method (Clopper-Pearson, 1934).

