5. STATISTICAL METHODOLOGY

5.1 General Considerations

All statistical evaluations will be conducted using SAS® version 9.4 or higher (SAS® Institute, Cary, North Carolina). All tables, figures and listings will be produced in landscape format.

In general, all data will be listed by subject and visit/time point where appropriate. The total number of subjects under the stated population (N) will be displayed in the header of summary tables.

Data will be summarized using descriptive statistics for continuous variables. Unless otherwise specified, descriptive statistics will include number of subjects, mean, standard deviation, minimum, median and maximum. In case of n<2, where n indicates the number of evaluable subjects at the particular time point, the standard deviation will be empty. The statistic "Missing" will also be presented as the number of missing entries/subjects, if any at that visit/timepoint, and presented as a summary statistic only when non-zero. The minimum and maximum statistics will be presented to the same number of decimal places as the original data. The mean and median will be presented to one more decimal place than the original data, whereas the standard deviation will be presented to two more decimal places than the original data.

In summary tables of categorical variables, counts and percentages will be used. The count [n] indicates the actual number of subjects with a particular value of a variable or event, which should always be less than or equal to the total number of subjects with non-missing value of the variable or event [M]. Percentage will be obtained by: % = (n/M)*100. Unless otherwise stated, all percentages will be expressed to one decimal place.

In by-visit summary tables only scheduled visits/timepoints will be summarized. In listings all visits and timepoints with any data collected, including both scheduled and unscheduled ones and early termination visits, will be included.

The closest non-missing measurement (whether from scheduled or unscheduled visit) taken prior to the administration of the study drug (PHO) will be considered as the baseline value. The change from baseline values will be derived for each subject as the post-baseline evaluation minus the baseline evaluation.

Study days will be calculated as the number of days from the date of the study drug administration:

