6. CHANGES IN ANALYSIS FROM PROTOCOL

There are no changes from the protocol-specified analyses.

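### As written, early-termination examinations enter neither physical-examination table, and early-termination laboratory values are left out of the laboratory descriptive statistics

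*SAP*

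**What the plan says.** **Protocol.** Section 5.3.2.2 covers subjects who leave for any reason other than withdrawing consent: "The investigator will make every effort to complete the following at the time of study discontinuation". The list that follows includes a comprehensive physical examination, vital signs, ECOG status and clinical laboratory tests. Under 5.3.2.1, nothing further is collected once consent is withdrawn. Section 10.5.3 asks for normal and abnormal findings "for each physical examination in a shift table comparing screening and the end of study evaluation". It also asks for laboratory descriptive statistics and a laboratory shift table at baseline and at the end-of-study assessment. Section 4.7 says that leaving early does not by itself take a subject out of the safety analyses.

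**SAP.** Section 5.1 states: "In by-visit summary tables only scheduled visits/timepoints will be summarized". Listings, by contrast, are to show all visits, "including both scheduled and unscheduled ones and early termination visits, will be included". The denominator rule is "Percentage will be obtained by: % = (n/M)*100", where M counts subjects with a non-missing value. Section 5.4.11.3 states: "Comprehensive physical examination will be performed at Screening and Study Exit Visits". Findings are summarised by visit, and then: "Additionally, a shift table comparing the Screening and Study Exit evaluations will be created". Section 5.4.11.2 summarises laboratory values by visit but runs the laboratory shift table to each subject's latest post-baseline value. Section 5.4.11 says that safety data are to be tabulated as well as listed. Section 6 states: "There are no changes from the protocol-specified analyses".

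**The concern.** After Screening, the schedule contains one physical examination, at Study Exit. A subject who stops earlier therefore has a single post-baseline examination, the one done at early termination, and the SAP gives it no place in either physical-examination table. Protocol 4.7 lists intolerable or serious adverse events and clinically significant laboratory values among the reasons for stopping, so the missing examinations may be informative. SAP 4.1 names physical examination and laboratory data among the primary endpoints. In a study of about 10 subjects, one absent examination changes a tabulated percentage visibly. Two neighbouring sections of the SAP also treat the same subject differently: the laboratory shift keeps the early leaver and the physical-examination shift does not.

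**Working it through.** **1. Who is affected.** Subjects in the Safety Population (they received the injection) who discontinue before Study Exit for a reason other than consent withdrawal and who had the early-termination assessments done. Consent withdrawals have no early-termination data to lose.

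**2. Where an early-termination assessment goes under the SAP as written.**

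| Assessment | By-visit table | Shift table | Listing |
|---|---|---|---|
| Physical examination | No (5.1) | No: Study Exit is named, with no mapping from early termination (5.4.11.3) | Yes |
| Laboratory | No (5.1) | Yes: latest post-baseline value (5.4.11.2) | Yes |
| Vital signs | No (5.1) | None planned | Yes |
| ECOG | No (5.1) | None planned | Yes |

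**3. Comparison with the protocol.** Protocol 10.5.3 ties three summaries to the end of study: the physical-examination shift, the laboratory descriptive statistics and the laboratory shift. Under the SAP the first two lose early-termination data and the third keeps them. The protocol ties no vital-sign or ECOG summary to the end of study.

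**4. Size.** Neither document gives a dropout rate or an abnormality rate, so the following is illustration only. Assume 10 treated subjects and d early leavers, all examined at early termination. Let a be the number of abnormal completers and e the number of abnormal early leavers.

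- Study Exit only: a / (10 − d)
- Early-termination examination included: (a + e) / 10

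| d | a | e | Study Exit only | Early termination included |
|---|---|---|---|---|
| 1 | 0 | 1 | 0/9 = 0% | 1/10 = 10% |
| 2 | 0 | 2 | 0/8 = 0% | 2/10 = 20% |
| 3 | 0 | 3 | 0/7 = 0% | 3/10 = 30% |
| 2 | 1 | 0 | 1/8 = 12.5% | 1/10 = 10% |

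The first three rows are the extreme case: every leaver abnormal and every completer normal. The last row shows that the direction is not fixed. If the leavers are normal, leaving them out raises the percentage.

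**5. The plan's own figure.** The only computed design figure is the table of one-sided 95% exact upper limits for 0 to 5 events in 10 subjects (SAP 3.1). Solving P(X ≤ x | n = 10, p) = 0.05 for p gives 0.2589, 0.3942, 0.5069, 0.6066, 0.6965 and 0.7776. These agree with the printed values to two decimals. This point does not touch that table.

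**The case against.** There is a good deal to say for the SAP, and most of it stands.

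- **Early leavers are not lost from the safety analysis.** They stay in the laboratory shift table, in the adverse-event tables (including the count of events leading to discontinuation), in disposition and in every listing. They also stay in the row of each scheduled visit they attended, such as the Day 5 laboratory tests. Protocol 8.4.1 requires adverse events to be documented from examination findings and laboratory values too, so an important abnormality should reach the adverse-event tables. With about 10 subjects, the listings can be read in full.
- **Limiting by-visit rows to scheduled visits is ordinary practice.** For vital signs and ECOG it contradicts nothing in the protocol.
- **Exclusion from the shift table is inferred.** The SAP names Study Exit and does not say whether an early-termination examination may count as that visit. Exclusion is still the natural reading: SAP 5.1 treats early termination as a distinct kind of visit, and the laboratory section says so when the latest value is wanted.
- **The protocol does not define its end-of-study evaluation.** The heading of Protocol 5.3 covers completers and early leavers alike, which suggests that both are meant. Protocol Appendix 13-1, however, places the post-baseline examination only at Study Exit. A reader might infer that the statement of no changes in SAP 6 is wrong. The documents support only an ambiguity there.

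What remains is that physical examination is listed separately among the SAP's primary endpoints and has its own protocol-specified shift table. Adverse-event tables and listings do not fill that table.

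**Conclusion.** The point holds in a limited form. As written, an early discontinuer's only post-baseline physical examination is listed but tabulated nowhere, and the early-termination laboratory values are absent from the descriptive statistics. That fits poorly with Protocol 4.7, with the statement in SAP 5.4.11 that safety data are tabulated, and with the SAP's own laboratory shift rule.

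The size is unknown. Each affected subject is 1 of about 10, and the percentages under working rest on assumed numbers of leavers and findings. A reader might infer that subjects who leave for toxicity disappear from the safety results, or that the tables are biased towards looking safe. The documents do not support either: the same subjects are counted in several other tables, no dropout rate is given, and the direction of the effect depends on findings that cannot be known in advance. The conclusion assumes that no programming specification outside these documents already maps early termination to Study Exit.

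**What to change.** 1. In SAP 5.4.11.3, define the shift as Screening to the latest post-baseline examination, meaning Study Exit or, for early discontinuers, the early-termination examination. This matches the rule already used for laboratory shifts in 5.4.11.2.
2. In SAP 5.4.11.2, add one end-of-study row (Study Exit or early termination) to the laboratory descriptive table, as an explicit exception to the scheduled-visit rule in 5.1. Leave the scheduled-visit rows unchanged.
3. Footnote both tables to say that the study day of the end-of-study value differs between subjects.

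If the sponsor prefers Study Exit only, SAP 5.4.11.3 and 5.4.11.2 should say so, and SAP 6 should record how this relates to the protocol's end-of-study wording. Similar rows for vital signs and ECOG are optional.

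The cost is a few sentences of SAP text, one table row and a footnote. Protocol 5.3.2.2 already asks for the data. The one drawback is that the end-of-study row mixes different lengths of follow-up, which the footnote discloses.

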5.4.11.4 Vital Signs

Vital signs (pulse, systolic and diastolic blood pressure, temperature, and respiration rate) will be collected at all visits. On Day 1, vital signs will be performed prior to Photofrin[®] injection and repeated at 15 and 30 minutes, 1, 2, 4, and 8 hours after injection. At other visits vital signs to be assessed once.

Actual values of vital signs and changes from baseline will be summarized using descriptive statistics by time point. Only subjects with both non-missing baseline and time point values will be summarized at each time point.

All vital signs data will be provided as a by-subject listing.

5.4.11.5 Prior and Concomitant Medications

Subjects may receive medication that is clinically indicated, such as pain prophylaxis, as per the investigator's clinical judgement. The brand name (or, if unknown, the generic name), dose, dose unit (or dosage form if compound), frequency, route of administration, duration of use (start date and, if applicable, stop date) and indication for all previous medications and concomitant medications must be documented in the concomitant medication record section of the case report form (CRF). Concomitant medications include intravenous fluids, herbal products, vitamins, and any over-the-counter medicines.

Prior medications are defined as those taken only before the date of informed consent, i.e. stopped before the date of informed consent. Concomitant medications are defined as any non-study medication taken during the course of the study i.e. on or after the date of informed

consent. Additionally, the medications will be considered concomitant if the stop date of the medication is missing (not available).

Prior and concomitant medications will be summarized by anatomical-therapeutic-chemical (ATC) classification (highest level available) and WHO Drug Dictionary preferred term.

Prior and concomitant medication information will be presented in a by-subject listing with ATC classification (highest level available) and WHO Drug Dictionary preferred term, start and stop date, dosage, route, frequency and indication.

5.4.11.6 Adjunctive Therapy/Procedures

An adjunctive therapy/procedure is defined as any procedure or intervention (e.g., psychotherapy, surgery, dental work, acupuncture, physiotherapy, chiropracty, osteopathy) used to treat an illness.

The adjunctive therapy/procedure (type, duration of use [start date and, if applicable, stop date], and indication) received during 30 days prior to the date of the ICF signature and throughout the study will be recorded in the adjunctive therapy record of the CRF.

Frequency of adjunctive therapies will be summarized descriptively by therapy type. All information will be listed.

5.4.12 Chest X-ray

Chest X-ray will be performed at Screening, if not done up to 90 days prior to the visit, as well as at the Hospital Discharge and Day 20-25 visits. X-ray will be classified as normal or abnormal. Number and percentage of subjects with normal and abnormal findings will be presented by visit. All findings will be listed.

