## 4. STUDY POPULATION

### 4.1. Primary Diagnosis

This study plans to enroll subjects with histologically or cytologically confirmation of peripherally located solid tumor in lung parenchyma. When applicable, subjects will be staged with chest CT and positron emission tomography (PET) scanning or as per local practice. Ideally subjects should have undergone an initial integrated whole body PET CT scan as part of their standard of care (SoC) staging protocol.

All procedures performed to confirm the primary diagnosis will be considered SoC and not research-related activities and will be performed no more than 60 days prior to ICF signature. Primary diagnosis will be based on the following assessments as per local practice and physician's clinical judgement to avoid unneeded procedures.

1. Confirmed solid tumor.
2. Either biopsy- or cytology-proven confirmation of primary or metastatic lung tumor of any subtype (e.g., adenocarcinoma, carcinoids, squamous cell carcinoma, large cell carcinoma, NOS [not otherwise specified], etc.).
3. Peripheral tumor location as defined by the Radiation Therapy Oncology Group protocols as the primary tumor not touching a 2-cm volume in all directions around the proximal bronchial tree (distal 2 cm of the trachea, main stem bronchi, and lobar bronchi). Tumors beyond the 3rd generation airways are included.
4. Tumor < 5 cm along any axis based on official radiology report.
5. Candidate for surgery.

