#### 5.1.2. Screening Procedures

Before any study-specific procedures are performed, informed consent will be obtained (Section 5.1.1). All subjects will undergo the following evaluations at the screening visit:

1. Review of eligibility criteria (including primary diagnosis);
2. Collection of demographic data;
3. Collection of medical and oncological history, including concurrent medical conditions;
4. Comprehensive physical examination as per SoC (excluding genital/gynecologic and urogenital unless indicated);
5. ECOG Performance Status (Appendix 13-2);
6. Skin phototype according to Fitzpatrick Classification (Appendix 13-3);
7. Vital signs (pulse, blood pressure, temperature, and respiration rate), body weight (SoC), and height assessment;
8. Chest X-ray if has not been performed up to 90 days prior to ICF signature;

9. A 5-minute resting 12-lead ECG if has not been performed up to 30 days prior to ICF signature;
10. Clinical laboratory (Appendix 13-4);
11. Serum  $\beta$ -HCG (only for female subjects of childbearing potential);
12. Collection of all adjunctive therapies/procedures and medication information including over-the-counter and phytomedicinal products currently taken by the subject as well as up to 30 days prior to the date of the ICF signature;
13. Collection of adverse events.

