## 10. DATA MANAGEMENT AND STATISTICS

### 10.1. Sample Size/Power Considerations

This study is designed to assess the safety of PDT in subjects with solid lung tumors prior to surgical resection and to assess the lung tumor and healthy tissue response to PDT. The intent of this study is to enroll 10 subjects. This sample size has the following precision for estimation of rates of AE's of special interest (AESI). The following table shows historical AE rates for RFA ranging from <1 to ~50%.

AESI	Rate observed with RFA
Pneumothorax	11-52%
Pleural effusion	6-19%
Hemorrhage	6-18%
Pulmonary artery pseudoaneurysm	0.2%
Needle tract seeding	0.3-0.7%
Cavitation	14%
Bronchopleural fistula	0.6%
Pneumonitis	0.4%

The sample size of N=10 has precision for estimation of AE rates for estimates ranging from <0.01 to ~0.5 as shown in the following list. Precision is measured by 1-sided 95% upper confidence limit (CL) on the estimated AE rate *via* exact binomial distribution. PDT is expected to have lower AE rates than RFA, so, for example, for a RFA historical rate of 0.27 (27%), if no such AE's are observed on PDT, then the TRUE underlying PDT rate is lower than 0.27 with 95% confidence since the upper 95% CL is 0.26 - indicated by "\*" in the list below.

No. of AESIs	Rate	Upper 1-sided 95% confidence limit
0	0.00	0.26*
1	0.10	0.39
2	0.20	0.51
3	0.30	0.61
4	0.40	0.70
5	0.50	0.78

The study will be suspended and re-evaluated from a safety standpoint if 20% of the subjects experience a serious adverse event that is related to PDT.

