5.4.13 Other Assessments

12-lead ECG will be performed at screening if not done up to 30 days prior to the informed consent. Results will be listed.

Light challenge will be performed by subjects at home prior to Day 43-48 visit. Results will be listed.

Information on unanticipated events (physical risk, psychological risk, economic risk, social risk, other) will be collected throughout the study. Results will be listed.

CT scan will be performed prior to surgery and at the Day 43-48 and Study Exit visits. Findings will be listed.

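### Chest X-rays are tabulated only as unpaired normal/abnormal counts and CT findings are only listed, so the imaging summaries separate new post-PDT findings poorly from the tumor and the resection

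*SAP*

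**What the plan says.** **Chest X-ray.** SAP 5.4.12 places films at screening (unless a recent one exists), "as well as at the Hospital Discharge and Day 20-25 visits". Each film gets one of two labels, and the output is a count of those labels: "X-ray will be classified as normal or abnormal. Number and percentage of subjects with normal and abnormal findings will be presented by visit". Individual findings also go into a listing. There is no shift table and no breakdown by type of finding.

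**CT.** SAP 5.4.13 reads: "CT scan will be performed prior to surgery and at the Day 43-48 and Study Exit visits. Findings will be listed". No summary is planned. Protocol Appendix 13-1 and SAP section 8, Table 1, both put CT at Day 13-18, Day 43-48 and Study Exit. All three follow PDT on Day 3, and the last two follow surgery. The 13 screening procedures in Protocol 5.1.2 include no CT.

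**Imaging before PDT.** Protocol 5.1.2 requires a screening film on this condition: "Chest X-ray if has not been performed up to 90 days prior to ICF signature". Protocol 4.1 leaves staging by chest CT and PET to applicability or local practice, allows the diagnostic work-up to date from up to 60 days before consent, and states: "All procedures performed to confirm the primary diagnosis will be considered SoC and not research-related activities". Tumor size must come from an official radiology report. SAP 5.4.4 summarises that size at baseline but pairs it with nothing later.

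**Extra film.** Protocol 5.2.1.3 calls for a further chest X-ray on the day of discharge when the hospital stay is extended because the subject is not medically stable.

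**The concern.** The label normal/abnormal carries little information when everyone enters with a lung tumor of up to 5 cm and everyone is planned for lung resection 10 to 15 days after PDT. A subject called abnormal at screening because of the tumor remains abnormal if a pneumothorax or effusion appears on Day 5. The Day 20-25 film comes after surgery. Because the counts are by visit and not paired within subject, a change in one subject can also be offset by an opposite change in another.

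The pre-surgery CT is the one scheduled CT that follows PDT and precedes resection. It has no baseline in the study data and no summary. A cavity or effusion seen on it is not set against an earlier image in any planned output.

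The sample-size section (Protocol 10.1, SAP 3.1) uses pneumothorax, pleural effusion, cavitation and pneumonitis among the events that motivate N=10. These are largely imaging findings, and they are what a reader would look for in the imaging tables.

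**Working it through.** **The plan's own figures.** The plan gives no figure for imaging. Its only statistical figures are the one-sided 95% exact upper limits for 0 to 5 events in 10 subjects. Computed as the 0.95 quantile of Beta(x+1, 10-x), they are 0.2589, 0.3942, 0.5069, 0.6066, 0.6965 and 0.7776. All six match the stated values to two decimals and are not in dispute.

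**How many new findings could the X-ray table show?** Inputs:
- n = 10 (Protocol 10.1, SAP 3.1).
- p = rate of a new finding on the Day 5 film. Assumed 0.11 to 0.52, the RFA pneumothorax range in Protocol 10.1.
- v = share of screening films already abnormal. Not in the documents, so a range is shown. Whether a new finding occurs is taken as independent of the screening label.

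Expected new findings: 10 × p = 1.1 to 5.2. Only subjects with a normal screening film can change category, so:
- expected visible changes = 10 × p × (1 − v);
- chance of at least one visible change = 1 − (1 − p(1 − v))^10.

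| v | Expected visible changes, p = 0.11 to 0.52 | Chance of at least one |
|---|---|---|
| 0 (every new finding visible) | 1.1 to 5.2 | 0.688 to 0.999 |
| 0.5 | 0.55 to 2.6 | 0.432 to 0.951 |
| 0.7 | 0.33 to 1.56 | 0.285 to 0.817 |
| 0.9 | 0.11 to 0.52 | 0.105 to 0.414 |
| 1 | 0 | 0 |

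The RFA range may be high. Protocol 10.1 expects lower rates with PDT, and Protocol 1.2 cites about 6% pneumothorax for navigational bronchoscopy. At p = 0.06 the expected number of new findings is 10 × 0.06 = 0.6, and the visible changes are 0.6 × 0.5 = 0.30 at v = 0.5 and 0.6 × 0.3 = 0.18 at v = 0.7.

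**How old can the comparison image be?** These are maxima, not typical values.
- Screening X-ray: 90 days before consent plus up to 30 days of screening = about 120 days before enrollment.
- Diagnostic imaging: 60 + 30 = about 90 days before enrollment, and 90 + 13 to 90 + 18 = about 103 to 108 days before the pre-surgery CT.

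**How other data are handled.** SAP 5.4.11.2 and 5.4.11.3 give laboratory results and physical examination a shift table. SAP 5.1 defines baseline as the closest non-missing measurement before the drug. Neither device is applied to imaging.

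**The case against.** The strongest reply is that one count table is not the only place these findings appear.

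- SAP 5.4.12 and 5.4.13 list all X-ray and CT findings by subject, and ten subjects can be read one by one. This stands. But the listing sets no pre-PDT CT beside the pre-surgery CT, because none is scheduled.
- Protocol 8 requires all adverse events to be recorded whatever their relatedness or clinical significance, and 8.4.1 draws them from any CRF data. SAP 5.4.11.1 counts them by preferred term with exact upper limits and adds the NCS events. A Day 5 pneumothorax recorded this way is counted by name. This also stands. The limit is that the treatment-emergent table covers everything from injection to study exit, so PDT-period and post-resection events are pooled. Onset dates appear only in the listing.
- Tissue response is defined by cytology and pathology (SAP 4.2), so imaging does not bear on it.
- Radiology reports are reviewed for eligibility, so an investigator can often judge whether a finding is new. This is fair, though a prior CT is not guaranteed and no output records the comparison.

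A reader might go further and infer that the X-ray table would look the same whatever PDT did, or that 70-100% of new findings would be lost. The documents do not support either. The first holds only at v = 1. The second merely restates an assumed v of 0.7 to 1.0; no share is given, and there is no minimum tumor size from which to argue that nearly all screening films are abnormal. Nor is Day 5 always the only film soon after PDT, since subjects with an extended stay have another at discharge.

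**Conclusion.** The concern holds as a weakness of the supportive imaging summaries. The X-ray table cannot register a new Day 5 finding in a subject already classed as abnormal, and it never names a finding. The pre-surgery CT is neither summarised nor paired with an earlier image. PDT-period and post-resection findings are therefore harder to tell apart than they need be.

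The share of new findings that the table misses equals v by construction. The numerical size rests on that assumed share and on the borrowed RFA rates; the structural gap does not. It does not follow that the trial would miss these events: the listings and adverse event tables remain, and neither the primary nor the secondary endpoint is compromised. The change is worth making because it is cheap and uses images and reports that largely exist already.

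**What to change.** **SAP 5.4.12.** Add, or substitute for the normal/abnormal table, a table of new or worsened findings against the latest available pre-PDT image, by type: pneumothorax, effusion, infiltrate/pneumonitis, cavitation, other. Report it at Day 5 and for any extended-stay discharge film. Label Day 20-25 as post-resection.

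**SAP 5.4.13.** Where a standard-of-care chest CT from before PDT exists, record its findings as baseline. Tabulate new findings on the pre-surgery CT against it, separately from the two post-resection CTs. Show subjects without one as 'no baseline CT'.

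**Reconcile the screening film window.** SAP 5.4.12 counts 90 days back from the visit, whereas Protocol 5.1.2, Protocol Appendix 13-1 and the SAP's own schedule table count from consent signature.

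**Cost.** SAP wording and a few CRF fields completed from existing reports; no added scan. The SAP is dated April 10, 2018 and enrollment was planned to run to Q1 2018, so entry may be retrospective. Some reports may not state a comparison, and some baselines will be missing.
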